12.8. Blinding and code-breaking

Due to the nature of the DD+ intervention and the usual care control group, patients cannot be blinded to the intervention. Researchers responsible for recruitment, screening, baseline assessment, and scheduling intervention appointments will be unblinded. Researchers conducting outcome evaluations will be blinded to participant allocation, and participants will be instructed not to disclose details of their allocation to the research team at any time during the study.

Blinded statisticians will perform statistical analysis. Qualitative interviews and analysis will be conducted by unblinded researchers.

12.9. Description of study intervention

DD+ consists of a patient-centred assessment whereby the clinician invites the patient to rate their satisfaction with different life domains and treatment aspects. This is followed by a four-step solution-focused approach to identify the patient's resources and develop solutions to deal with the patient's concerns. The intervention is available as an app and makes use of a tablet computer (e.g. ipad or android device) within routine clinical meetings.

Each session begins with the patient using the tablet to rate their satisfaction with eight life domains (mental health, physical health, job situation, accommodation, leisure activities, friendships, relationship with family/partner, personal safety) and three treatment aspects (medication, practical help, meetings with professionals). The tablet allows patients to be more actively involved in the meeting, with the tablet easily passed between the clinician and patient. Each satisfaction item is rated on a scale from 1 ("totally dissatisfied") to 7 ("totally satisfied"), and followed by a question on whether the patient wants additional help with that domain. The ratings are summarised on screen, allowing for comparisons with ratings from previous meetings. Clinicians are instructed to offer positive feedback on any improving or high-scoring domains.

The ratings are followed by a four-step solution-focused approach to identify the patient's existing resources that can be used to address the concerns raised. The four steps are: Understanding (Why is the patient dissatisfied? What went nevertheless well?); Looking Forward (What is the best-case scenario? What is the smallest step forward?); Exploring Options (What can the patient, the clinician or others do?); and finally Agreeing on Actions (e.g. homework and referrals).

DD+ will be delivered by a blinded trial member once a month for six months in a specific appointment for this purpose.

The control group will continue their routine care in the health centre as indicated by the HC clinical team.

12.10. Subsequent Visits

Participants will be followed up at predefined time points as outlined in **Table 2**. Each visit will be identified by name and visit number and associated with the specific time window, when applicable. Details of each visit, including type, timing, and procedures, are described below.

Unless stated otherwise, all scales or instruments should be completed directly in REDCap. In the event of unforeseen circumstances, a paper-based CRF can be used. When using paper forms, the researcher in charge of data collection must enter or upload the completed scale or instrument into REDCap as soon as possible, and no later than two working days after collection.

Visit 0- Invitation and pre-screening

As mentioned in Section 12.1 (Recruitment), potential participants may be invited through waiting room invitation, practitioner referral, or study advertisements. Upon acceptance, potential participants will meet individually with a researcher to sign the consent form and complete the eligibility screening. The procedures described from visit 1 onwards apply to all participants, irrespective of any previous known diagnosis.

Visit 1 – Screening Visit

The screening visit is the initial assessment of the participant by the research team, excluding any previous communications intended to invite the potential participant or arrange the time for visit 1. The place of the visit will correspond to each of the participating HCs. The first activity in the screening visit will be the delivery of the information about the trial as a formal invitation for the participant. If interested, the researcher will proceed with the informed consent procedure, broadening the information about study aims and procedures. Upon acceptance and signing of the informed consent, the following procedures will take place for all participants irrespective of previous diagnosis status:

- The MANSA scale will be completed by the participant with the researchers' aid. A MANSA score of five or less points is a prerequisite for continuing in the trial, as stated in the inclusion criteria.
- The researcher will complete mental health screening scales through patient interview (PHQ-8, GAD-7, AUDIT-C).
- The researcher will screen participants for diabetes, obesity and HBP following standard procedures. The diagnosis will be assessed based on the in-situ screening or a previously reported and confirmed diagnosis by the healthcare provider. Screening criteria are presented in **Table 3**.
 - a. The researcher will take a capillary blood sample for assessing HbA1c levels ([Afinion™ HbA1c Abbott](#)),
 - b. Measure blood pressure with standard electronic equipment. During the visit, the assessment will be done at three moments, with at least five minutes between measurements. HBP measurement will follow the checklist and recommendations from the 2025 AHA Guideline for the Prevention, Detection, Evaluation, and Management of HBP, as well as the established study standard procedures (46).

- c. Record abdominal circumference measuring at the midway between the bottom of the ribs and the top of the hips, while the participant breathes out naturally, before taking the measurement (47).
- d. Record height and weight using validated instruments and as stated in the standard procedures.

The screening visit is finalised with the determination of the participant's eligibility. The assessment will be made by the researcher after filling out the selection criteria checklist.

Visit 2- Baseline Assessment Visit

Depending on logistical issues and the availability of the research team and participants, the screening visit and baseline assessment may be performed on the same day or a different day, considering a window of no more than ten calendar days. The baseline consists of the completion of a sociodemographic questionnaire and the remaining instruments for this visit (EQ5D, WHOQOLBREF, SIX, CSRI). The researcher will complete the baseline assessment through a patient interview. This process will take approximately 60 minutes. Visit 2 finalise with participant randomisation.

Visits 3 to 8 – Intervention visits

After randomisation, visits 3 to 8 will take place once a month (average month duration of 30 calendar days), with a 10-day window.

- Patients will be assigned to a routine clinical visit with a trial clinician. The local trial research coordinator will facilitate the appointment assignment.
- A member of the research team will accompany the patient and clinician to support them in any technical or logistical issues.
- Patient and clinician will privately go through the intervention meeting: DD+ with the solution-focused approach.

At visit 6, a researcher will update the CSRI with participants, either at the health centre during the DD+ intervention visit or by phone within five days after the visit.

Visits 3 to 8 – Control group follow-up

Participants allocated to the control group will be followed up on monthly by phone call to assess any health events, and to remind the 6-month follow-up visit.

Visit 9- Main and secondary 6-month outcome assessment.

Within 30 days after Visit 8, a researcher will schedule Visit 9 with participants. The researcher will complete the clinical scales described in Table 1 through patient interviews. Also, HbA1c, HBP and abdominal circumference will be reassessed. For the qualitative implementation assessment, twenty-four patients will be sampled and interviewed as defined in Section 13. Semi-structured interviews will be audio-recorded and are expected to last between 30 and 60 minutes.

Visit 10 and 11- Maintenance period intervention visits

At 90 (± 10) days from visit 9 (visit 10) and 90 (± 10) days from visit 10 (visit 11), participants in the intervention arm will go through the DD+ intervention.

Visits 10 and 11 – Control group follow-up

At 90 (± 10) days from visit 9(visit 10) and 90 (± 10) days from visit 10 (visit 11), participants in the control arm will receive a follow-up phone call.

Visit 12- Main and secondary 12-month outcome assessment

At ± 10 days after visit 11, a researcher will schedule visit 12 with participants. The researcher will complete clinical scales and CSRI through patient interviews. Visit 12 will be the last study visit.

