- c) During the trial recruitment period, FIM, IAM, and AIM scales will be administered to clinical and managerial leaders from each health centre and to the staff responsible for delivering the intervention. These data will be complemented with semi-structured interviews to enhance explanatory power and to assess additional implementation criteria, including fidelity and adoption.
- d) After the 6-month assessment, clinical and managerial leaders, as well as the staff responsible for delivering the intervention, will again complete the FIM, IAM, and AIM scales, together with a complementary semi-structured interview.

Methods and procedures for the effectiveness assessment are presented in the following sections. Details on the implementation context assessment are provided later in Section 13. **IMPLEMENTATION CONTEXT ASSESSMENT**. The full set of procedures for patients is described in the effectiveness section as an integral guide to study activities, in order to avoid mistakes or confusion during data collection.

Figure 1. Study Phases Overview

Abbreviations: AIM= Acceptability of Intervention Measure; IAM= Intervention Appropriateness Measure; FIM= Feasibility Intervention Measure, Int= Intervention Dynamic DIALOG+(DD+).

v2.0-30 November 2025 BOND+ TRIAL T1_CO_PROTOCOL_Ethics_20251024_v2.0_Control_EN

Table 2. Summary of study visits procedures for patients

| Month | | | M1 | M2 | M3 | M4 | M5 | M6 | M6 | M9 | M12 | M12 | |
|---------------------------------------|---|------------|-----------|----------|-------------|--------------|---------------|--------------|-------------|---------|-----------|--------------|----------|
| Reference date for window calculation | | | Screening | Baseline | Int. I +30D | Int. II +30D | Int. III +30D | Int. IV +30D | Int. V +30D | Int. VI | 6-MA +90D | M.Int I +90D | M.Int II |
| Window (days) | | | +10 | ±10 | ±10 | ±10 | ±10 | ±10 | ±10 | ±15 | ±10 | ±10 | ±10 |
| Study visit name | | Screening* | Baseline* | Int. I | Int. II | Int. III | Int. IV | Int. V | Int VI | 6-MA | M.Int I | M.Int II | 12-MA |
| Study visit number | 0 | 1 | 2 | 3 | 4 | 5 | 6 | 7 | 8 | 9 | 10 | 11 | 12 |
| Invitation | X | | | | | | | | | | | | |
| Informed consent | | X | | | | | | | | | | | |
| MANSA QoL | | X | | | | | | | | X | | | X |
| WHOQOLBREF | | | X | | | | | | | X | | | X |
| EQ5D | | | X | | | | | | | X | | | X |
| Socio-demographics | | | X | | | | | | | | | | |
| PHQ-8 | | X | | | | | | | | X | | | X |

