| Acceptability of Intervention Measure (AIM) - Score | Interval | Comprises 4 items assessing the acceptability of an intervention: approval, appeal, liking, and welcoming of the intervention. Each item is rated on a 5-point Likert scale: 1 (Completely disagree) to 5 (Completely agree). Total score is calculated by averaging the item scores. | Baseline, 6 months |
| Intervention Appropriateness Measure (IAM) - Score | Interval | Comprises 4 items assessing the perceived appropriateness of the intervention: whether it seems fitting, suitable, applicable, and a good match. Rated on a 5-point Likert scale: 1 (Completely disagree) to 5 (Completely agree). Total score is calculated by averaging item scores. | Baseline, 6 months |
| Feasibility of Intervention Measure (FIM) - Score | Interval | Comprises 4 items assessing the feasibility of the intervention: whether it seems implementable, possible, doable, and easy to use. Items are rated on a 5-point Likert scale: 1 (Completely disagree) to 5 (Completely agree). Scores are averaged across items to obtain a total score. | Baseline, 6 months |
| Feasibility of Intervention Completion | Ratio | Feasibility was measured as the proportion of participants who agreed to participate, provided informed consent, were allocated to the active treatment, and completed the intervention as planned, relative to all those who initially agreed to participate and consented. | 6 months |
| Death status | Nominal | Has the individual passed away by the end of the follow-up period? (Yes/No). This is essential for determining the QALY value, as it implies a quality-of-life value of 0 for that individual. | 12 months |
| Costs of health service use, medication and productivity lost. Out-of-pocket expenses. | Ratio | In the CSRI instrument, we collect participants' use of inpatient hospital service, use of health care services, current medication, family support, out-of-pocket expenses and employment. | Baseline, 6 months, 12 months |
| Costs of DIALOG+, and costs of supervision and training to health professional | Ratio | The Health Economics Inventory forms | Training phase, implementation and monthly in the intervention arm. The research team will calculate costs. |

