16. STUDY LIMITATIONS AND BIAS CONTROL

Due to the diversity of settings in terms of geographic location and sociodemographic characteristics, the risk of bias due to lack of representativeness of the Colombian population will be low. The randomisation procedure is also expected to generate balanced groups, reducing the risk of differential selection bias and minimising the chances of differential losses. However, since participants in the control group will have less contact with the study team and will be aware of their allocation due to unblinding, there is a risk of higher losses in this group. To mitigate this, routine phone calls will be made to control participants as reminders for the 6- and 12-month follow-up assessments.

A risk of contamination bias exists due to the public availability of the DIALOG+ application in the Play Store. However, for the active group, the intervention will be delivered by a trial clinician in the intervention appointments. In contrast, the follow-up visits for the control group will be through brief phone calls. Neither the trial clinician nor the researcher in charge of the follow-up call will be part of the patient care team. Furthermore, the fact that the application is publicly available will not be explicitly disclosed to participants to minimise the risk of bias.

The lack of blinding may also introduce bias through QoL outcome overestimation. However, outcome assessors and statisticians will remain blinded to allocation to reduce the risk of overestimating the effect or its magnitude. The risk of allocation concealment failure exists, but it is limited because the allocation will be automatically provided by the REDCap platform and only disclosed at the end of the baseline assessment visit.

A risk of outcome misclassification also exists. Although the diagnostic scales and tests used are validated and widely applied, the absence of measurement errors cannot be guaranteed. However, any misclassification is not expected to be differential. Finally, the risk of confounding is low due to randomisation, but not negligible. Therefore, statistical analyses for primary and secondary outcomes will adjust for relevant covariates, and the interpretation of results will consider the distribution of known variables among intervention and control groups.

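### Section 12.10 adds a CSRI update at visit 6 that is tied to a DD+ session and has no control-arm counterpart, while Table 2, Table 7 and section 15.11.1 schedule the CSRI only at baseline, 6 and 12 months

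*Protocol*

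**What the plan says.** Section 12.10 describes visits 3 to 8 separately for each arm. Under the intervention-visit heading it says: "At visit 6, a researcher will update the CSRI with participants, either at the health centre during the DD+ intervention visit". A telephone contact up to five days later is allowed instead. Under the control heading for the same visit numbers, participants are "followed up on monthly by phone call to assess any health events, and to remind the 6-month follow-up visit". Section 16 describes the control contacts in the same way: "routine phone calls will be made to control participants as reminders for the 6- and 12-month follow-up assessments".

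The other places that schedule the CSRI are:

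- Section 12.10, Visit 2, and section 12.6 put the CSRI in the baseline assessment of all participants.
- Section 12.10, Visit 9 (the 6-month assessment) says: "The researcher will complete the clinical scales described in Table 1 through patient interviews". It does not name the CSRI.
- Section 12.10, Visit 12 says: "The researcher will complete clinical scales and CSRI through patient interviews".
- Table 2 marks the CSRI at visits 9 and 12 and once at the start of the study. It has no mark at visit 6.
- The cost row of Table 7, which describes the content of the CSRI, ends: "out-of-pocket expenses and employment. | Baseline, 6 months, 12 months".
- Section 15.11.1 sets the same three time points for resource use and says that they apply under DD+ and under usual care alike. It computes cost per participant over 0-6 and 0-12 months.

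**The concern.** The CSRI supplies the self-reported service use, medication and out-of-pocket spending behind the cost per participant, and so behind the incremental cost and the ICER. A comparison of self-reported use between arms needs the same number of interviews, at the same times and by the same method. The visit-6 sentence departs from this in one arm.

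An extra interview partway through months 0-6 could catch contacts that would otherwise be forgotten, or correct ones that would be over-reported. Either way, the difference in recorded cost would come from measurement and not from DD+. Randomisation does not remove it, and no analysis can supply a control interview that never took place.

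There is also a blinding aspect. Section 12.8 has outcome evaluations done by researchers who do not know the allocation. A researcher who updates the CSRI during a DD+ session necessarily knows it.

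**Working it through.** The protocol states no figure to reproduce here. The check sets the instructions side by side and counts contacts.

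**1. To whom the sentence applies.** Both options (at the session, or by phone within five days of it) are timed from a DD+ session. A footnote to Table 2 marks those sessions as intervention arm only. The control paragraph covers the same visit numbers and names only health events and a reminder. The natural reading is that only DD+ participants receive the update.

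**2. CSRI contacts per participant.**

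| Source | DD+ | Control |
|---|---|---|
| Table 2, Table 7, section 15.11.1 | baseline, 6 months, 12 months = 3 | baseline, 6 months, 12 months = 3 |
| The same, plus the visit-6 sentence read literally | 3 + 1 = 4 | 3 |

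**3. Where visit 6 falls.** Visit 6 is the fourth of the six monthly sessions; the 6-month assessment is visit 9. The reference-date row of Table 2 reads "Screening | Baseline | Int. I +30D | Int. II +30D | Int. III +30D".

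- If session I takes place at about day 0, visit 6 is at 3 × 30 = day 90 and visit 8 at 5 × 30 = day 150.
- If session I takes place one month after randomisation, visit 6 is at 4 × 30 = day 120 and visit 8 at 6 × 30 = day 180.
- Visit 9 follows within 30 days of visit 8, so it falls at day 150-180 or day 180-210.

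The gaps between CSRI contacts up to visit 9 are therefore:

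| Dating of session I | DD+, literal reading | Control |
|---|---|---|
| Day 0 | 90 days, then 60-90 days | one gap of 150-180 days |
| Day 30 | 120 days, then 60-90 days | one gap of 180-210 days |

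These are gaps between contacts and not recall periods. The protocol gives no CSRI recall period, and the patient CRF (Annex B) is not shown.

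**4. Could the sentence mean another visit?**

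- *Visit 9 (month 6).* The Visit 9 paragraph refers only to the scales of Table 1, and Table 1 does not list the CSRI, although Table 2 marks it there. A misplaced 6-month instruction would explain both anomalies. Contacts would then be 3 and 3. The wording would still be wrong, because visit 9 has no DD+ session.
- *The sixth DD+ session (visit 8).* This fits the reference to a DD+ session. The update would then come no more than about 30 days before visit 9, so any difference in timing between arms would be small.

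**5. After the correction.** Without the sentence, both arms have 3 contacts. With the update in both arms, each has 4.

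**The case against.** The strongest reply is that this is a drafting slip. No passage restricts the CSRI update to the DD+ arm, and the sentence itself speaks simply of participants. Section 15.11.1 covers both arms explicitly, Table 7 agrees, and section 12.10 opens by referring follow-up to Table 2. Three concordant schedules stand against one stray sentence. Section 15.11.1 also names only baseline, 6 and 12 months as its data, so a visit-6 record might never enter the cost totals.

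Much of this stands. The arm restriction is an inference from the heading, the link to the DD+ session and the silence of the control paragraph. It does not remove the point, because section 12.10 presents itself as the description of each visit's procedures and sites may follow it. On any of the three readings the text needs correcting: the update is unscheduled, or it refers to a session that does not exist at visit 9, or it carries the wrong visit number.

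A reader might infer more than this, and the documents do not support it:

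- *That the plan deliberately measures cost differently by arm.* Section 15.11.1 states the opposite intention.
- *That controls recall six months in one interview while DD+ participants do not.* Costing over 0-6 months does not tell us what period the questionnaire asks about.
- *That the bias can be given as a percentage of cost, or that it favours one arm.* This would need a recall error and a usual-care cost, and the protocol gives neither.

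**Conclusion.** The inconsistency is real and should be corrected before recruitment. Read literally, section 12.10 gives DD+ participants one CSRI contact more than controls (4 against 3) during months 0-6, possibly by a researcher who knows the arm. Resource use may therefore be recorded differently by arm in both costing periods, 0-6 and 0-12 months.

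The conclusion rests on the inference that the sentence applies to the DD+ arm and on sites following it as written. An effect on the cost totals further requires that the visit-6 information is used in them, or that it alters what is reported at visit 9. Sign and size are unknown, and the effect may be nil under the visit-9 reading. The MANSA analysis, the sample size and the clinical secondary outcomes are unaffected.

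**What to change.** Preferred: delete the visit-6 CSRI sentence from section 12.10 and name the CSRI in the Visit 9 paragraph for both arms, in the way the Visit 12 paragraph already does. The narrative then matches Table 2, Table 7 and section 15.11.1. The cost is wording only. The one thing given up is the mid-period update.

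If a mid-period update is wanted, do it by phone in both arms, at the same time after randomisation and with the same questions, and add it to Table 2, Table 7 and section 15.11.1. For controls it can be attached to the monthly call already planned at that visit, for up to 113 participants. It needs no new patients and no new visits. The protocol should not describe that caller as blinded: Table 2 marks the telephone follow-up as control arm only, so whoever makes the call knows the allocation.

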| GAD-7 | | X | | | | | | | | X | | | X |
| AUDIT-C | | X | | | | | | | | X | | | X |
| HbA1 measurement | | X | | | | | | | | X | | | X |
| HBP measurement | | X | | | | | | | | X | | | X |
| Obesity assessment | | X | | | | | | | | X | | | X |
| Eligibility checklist | | X | | | | | | | | | | | |
| SIX | | | X | | | | | | | X | | | X |
| CSRI | | | | X | | | | | | X | | | X |
| AIM | | | | | | | | | | X | | | |
| IAM | | | | | | | | | | X | | | |
| Dialog+** | | | | X | X | X | X | X | X | | X | X | |
| Telephone follow-up¥ | | | | X | X | X | X | X | X | | X | X | |
| Qualitative Interview¶ | | | | | | | | | | X | | | |

Abbreviations: M=Month; D=Day; Int= Intervention DIALOG+; M.Int = Maintenance Intervention DIALOG+; PHQ-8=Patient Health Questionnaire-9; GAD-7=Generalized Anxiety Disorder-7; HBP= High Blood Pressure; SIX=Objective Social Outcomes Index; CSRI= Client Service Receipt Inventory; AIM= Acceptability of Intervention Measure; IAM= Intervention Appropriateness Measure; FIM= Feasibility Intervention Measure; 6-MA: six months assessment.

*The screening visit and baseline visit may be performed on the same day or on a different day.

**Intervention arm only

¥Control arm only

¶A sample of 24 patients allocated to the intervention group will be interviewed. The window for qualitative interviews can be extended by 15 additional days beyond the indicated timeframe.

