13.3. Sample and sampling

13.3.1. Patients

The AIM and IAM instruments will be administered to all participants in the intervention arm. For the qualitative interviews aimed at assessing feasibility and providing additional explanatory depth for implementation outcomes, a purposive sampling strategy based on a maximum variation matrix will be used. This strategy will consider participants' adherence to intervention visits, age, and sex. Participants attending at least 3 out of 6 intervention visits will be classified as having high adherence, while those attending 2 or fewer visits will be classified as having low adherence.

Table 5 displays the maximum variation matrix for sampling patients for qualitative semi structured interviews. The number in each cell indicates the number of participants with those characteristics to be sampled.

Table 5. Maximum Variation Matrix

| | Male 18-24 | Female 18-24 | Male 25-44 | Female 25-44 | Male 45-65 | Female 45-65 |
|-----------------------------|---------------|-----------------|---------------|-----------------|---------------|-----------------|
| High adherence participants | 2 | 2 | 2 | 2 | 2 | 2 |
| Low adherence participants | 2 | 2 | 2 | 2 | 2 | 2 |

* The upper limit of each age interval includes participants up to that age plus 364 days.

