15.2. Sample Size Determination

The sample size calculation for this study will be based on parameters derived from previous DIALOG+ trials (35). A standard deviation of 0.9 for the MANSA and a correlation of 0.4 between baseline and follow-up measurements will be assumed, while an effect size of 0.4 points on the MANSA will be considered the minimal clinically important difference (MCID) for quality of life in this patient population. Based on these parameters, a total of 90 participants per group will be required to achieve 90% power at the 5% two-sided significance level. To account for an anticipated 20% attrition rate, the final sample size will be set at 226 participants (113 per group).

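### Reminder calls for the 6- and 12-month assessments are written for the control arm only, so outcome collection in the DD+ arm may depend on session attendance

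*Protocol*

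**What the plan says.** For Visits 3 to 8, section 12.10 states that the "control group will be followed up on monthly by phone call to assess any health events, and to remind the 6-month follow-up visit". It gives controls further calls at Visits 10 and 11, without stating their purpose. In Table 2 (section 10.1) the telephone row is footnoted "Control arm only". Section 16 expects higher losses among controls because they have less contact with the study team, and continues: "To mitigate this, routine phone calls will be made to control participants as reminders for the 6- and 12-month follow-up assessments". The 12-month reminder rests on this sentence, since section 12.10 mentions only the 6-month one.

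In the DD+ arm, the written contact before assessment is the sessions themselves, with appointments arranged by the local coordinator. In both arms a researcher schedules Visit 9 within 30 days after Visit 8. Visit 12 is timed from Visit 11.

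The protocol plans for poor attendance. Section 13.3.1 says "those attending 2 or fewer visits will be classified as having low adherence", out of six visits, and Table 5 seeks 12 such participants among the 24 interviewees. Section 15.3 promises an intention-to-treat analysis regardless of adherence. Section 15.4 imputes under missing at random from treatment group and baseline covariates, with a complete-case analysis as the only stated sensitivity analysis.

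**The concern.** The reason given for calling only controls, that they have less contact, holds for DD+ participants who attend. It does not hold for those who stop. A passive control still has eight scheduled calls (Visits 3 to 8, 10 and 11), and Visit 8 for a control is itself a phone call. A DD+ participant who stops has no written assessment reminder and no Visit 8 from which Visit 9 can be timed.

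The effort spent on collecting the outcome can therefore depend, in one arm only, on a post-randomisation variable. If non-attenders are lost more often and their MANSA differs from that of attenders with the same baseline, the observed DD+ mean is not that of the whole randomised arm, and the intention-to-treat comparison is biased. Imputation that uses only arm and baseline would fill the gaps mostly with values typical of attenders. The complete-case analysis rests on the same observed participants, so agreement between the two would not be reassuring.

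**Working it through.** **The plan's own figure.** Section 15.2 states: "A standard deviation of 0.9 for the MANSA and a correlation of 0.4 between baseline and follow-up measurements will be assumed". The target difference is 0.4 points, and "90 participants per group will be required to achieve 90% power at the 5% two-sided significance level". Attrition is 20%, one figure not split by arm.

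- Baseline-adjusted SD = 0.9 × √(1 − 0.4²) = 0.825.
- n per arm = 2 × [0.825 × (1.960 + 1.282) / 0.4]² = 89.4, rounded up to 90.
- 90 / 0.8 = 112.5, rounded up to 113 per arm, 226 in total.

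The stated sample size reproduces exactly, and nothing below changes it.

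**Bias from attendance-related loss.** The protocol gives no loss rate by attendance, so these inputs are assumptions:

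- q, the share of the DD+ arm who are non-attenders: 10% to 30%.
- Retention of DD+ attenders: 85%. Retention of controls: 80%, unrelated to outcome.
- r, the retention of DD+ non-attenders: 20%, 50% or 80%.
- g, the gap in 6-month MANSA between attenders and non-attenders after baseline adjustment: 0.2 to 0.6.

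Formulas:

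- DD+ retention R = (1 − q) × 0.85 + q × r.
- Non-attender share among those observed: q_obs = q × r / R.
- Bias in the DD+ mean = g × (q − q_obs).
- Standard error = 0.825 × √[1/(113R) + 1/(113 × 0.8)]. The type I error is that of a two-sided 5% test shifted by bias/SE when the true intention-to-treat difference is zero.

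Middle case (q = 20%, r = 50%, g = 0.4): R = 0.68 + 0.10 = 0.78; q_obs = 0.10/0.78 = 0.128; bias = 0.4 × (0.200 − 0.128) = 0.029.

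Upper case (q = 30%, r = 20%, g = 0.6): R = 0.595 + 0.06 = 0.655; q_obs = 0.06/0.655 = 0.092; bias = 0.6 × (0.300 − 0.092) = 0.125.

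| q | r | g | DD+ retention | Bias (points) | Share of 0.4 | Type I error |
|---|---|---|---|---|---|---|
| 10–30% | 80% | 0.2–0.6 | 83.5–84.5% | 0.001–0.008 | 0–2% | 5.0% |
| 10% | 50% | 0.2 | 81.5% | 0.008 | 2% | 5.0% |
| 20% | 50% | 0.4 | 78.0% | 0.029 | 7% | 5.6% |
| 20% | 20% | 0.4 | 72.0% | 0.058 | 14% | 7.4% |
| 30% | 20% | 0.6 | 65.5% | 0.125 | 31% | 16.2% |

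In the last row, power for a true difference of 0.4 falls to 87.2% through the smaller observed DD+ group alone.

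The sign of the bias follows the sign of g. The table takes attenders to do better. If people stop sessions because they feel well, g is negative and the bias runs against DD+.

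**The case against.** The asymmetry is reasoned. DD+ participants have monthly sessions and controls have none, so the calls bring contact in the two arms closer together, and the protocol expects the greater loss among controls.

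A reader might infer that DD+ participants who stop have no scheduled contact at all, or that the calls are the protocol's only retention measure. The documents do not support that. A researcher schedules Visits 9 and 12 without restriction by arm. The coordinator arranges session appointments. Section 12.4 confirms contact details at consent. Section 21.9 and Table 8 give every patient the same bonus, snack and transport at each assessment. The interview plan also shows an intention to keep low attenders in assessment at 6 months.

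It can further be said that 6 and 12 months are the nominal times for both arms (section 10.1), that the covariate list in section 15.4 leaves room for other relevant measures, and that tracing steps may sit in standard operating procedures not shown. The protocol does not forbid calling DD+ participants.

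Much of this stands, and it limits the point to something narrow. None of it supplies a written assessment reminder for DD+ that is independent of attendance, or a way to time Visit 9 when Visit 8 did not take place.

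**Conclusion.** The point holds as a risk in a rule that the protocol itself fixes by arm. Assessment reminders are specified for controls only, and in DD+ both the contact before assessment and the timing of Visit 9 lean on session attendance. The named imputation variables do not include attendance, and the stated sensitivity analysis would not show the problem.

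Size and direction are unknown. On the assumptions above, the bias is negligible if non-attenders are retained about as well as others, about 0.03 points in a middle case and 0.125 points at the upper end, against a planned 0.4. It becomes material only if most non-attenders are lost and their outcomes differ clearly.

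A reader might infer that MANSA will in fact be lost selectively and that the DD+ effect will be inflated by a definite percentage. The documents give no loss by attendance and no outcome difference between attenders and non-attenders, so neither inference is supported. This is an inexpensive improvement; it does not show that the primary result is compromised.

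**What to change.** - In section 12.10, Table 2 and section 16, specify the same reminder before Visits 9 and 12 for every participant in both arms, whatever the number of sessions attended. Limit the script to the assessment visit, and have it made by staff other than the blinded outcome assessors.
- Time Visits 9 and 12 from randomisation in both arms. Section 15.11.5 already describes the EQ-5D-5L time points in that way.
- In section 15.4, add number of sessions attended to the imputation model for the DD+ arm.

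Calls triggered by each missed session are best left out. Completing the intervention as planned is a feasibility outcome (Table 7, section 15.8), and such calls could influence it.

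Cost: 113 × 2 = 226 short extra calls in the DD+ arm and a little caller time, beside the 113 × 8 = 904 already planned for controls, whose calls at Visits 8 and 11 can carry the same script. If controls also receive separate reminder calls, the extra total is 452. The sample size stays at 226.
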